6.11.2 Sensitivity Analysis

The primary analysis will be repeated for the PPS.

Missing MELD data will be imputed using a last observation carried forward approach and the primary analysis will be repeated with the imputed data included.

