### **12.8.3 Secondary variables**

The secondary and exploratory efficacy variables will be summarised with descriptive statistics per treatment group and visit. The change from baseline to Day 28 (and other visits) for the active treatment group will be compared against placebo either via logistic regression or analysis of covariance taking the baseline level as covariate into account. Survival time will be analysed using the Cox Proportional Hazards model including treatment group and MELD score at baseline as covariate. The 5% level of significance will be used for all treatment comparisons of secondary and exploratory endpoints without adjustment for multiplicity.

A new secondary efficacy variable will be a 5-level ordinal variable combining change of MELD score from baseline, premature treatment terminations and mortality as follows; each patient will be allocated to the first level that occurs

- level 1: death within 28 days,
- level 2: death within 90 days,
- level 3: early treatment termination because of safety issues or lack of efficacy,
- level 4: no improvement in Meld Score at day 28 compared to baseline,
- level 5: improvement in Meld Score at day 28 compared to baseline

Patients with lost to follow up within 28 days will be allocated to level 4 or 5 according to their imputed result at day 28 based on the model in 12.9.2 as for these patients the MAR assumption seems appropriate.

This ordinal variable will be analysed using ordinal logistic regression with MELD score as baseline covariate ( $\alpha=0.05$  two-sided). An odds ratio including 95%-confidence limits will be calculated as measure of effect size for this variable.

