6.3 General Derivations

- Definition of baseline

Baseline is defined as the last non-missing value (including scheduled and unscheduled assessments) prior to the patient receiving study treatment.

- Incomplete dates

For calculation purposes, incomplete dates will be completed using worst case. Further details are detailed in the relevant sections as required.

- Non-numeric values recorded in a numeric field

In the case where a variable is recorded as “>x”, “ $\geq x$ ”, “ $<x$ ” or “ $\leq x$ ” in a numeric field, then for analysis purposes a value of x will be taken. Where a range of values is quoted the midpoint of the range will be taken. For example, if a laboratory safety parameter is reported as being below the limit of quantification or $< x$, the value of the limit will be used in the calculation of summary statistics. The recorded value will be reported in listings.

- Methods for handling withdrawals and missing data

Imputation of any data will be detailed in the relevant sections.

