6.4 Analysis Sets

The **Enrolled Set** includes all patients who provided informed consent irrespective of whether they received the study treatment.

The “**All Randomised Patients (RAN)**” consists of all patients who were assigned a randomisation number, irrespective of the treatment they received, if any. If this analysis set coincides with the full analysis set, it will be omitted from the tables and listings.

The **Full Analysis Set (FAS)** includes all randomised patients who receive at least one administration of study treatment. Patients will be analysed according to the treatment they are assigned to at randomisation, irrespective of what treatment they actually received.

The **Per-Protocol Set (PPS)** will be a subset of the Full Analysis Set consisting of those patients who:

1. Complete 80% of the study treatment from baseline to day 28 or early termination visit and do not miss more than 3 consecutive days of dosing (or 6 consecutive doses)
2. Have complete MELD score data at baseline and day 28/early termination visit.
3. Do not have major protocol deviations considered having a serious impact on the efficacy results.

All protocol deviations will be assessed and documented on a case-by-case basis prior to the database lock, and major deviations considered having a serious impact on the efficacy results will lead to the relevant patient being excluded from the set. Major protocol deviations considered having a serious impact on the efficacy results include but are not limited to:

- Patients failing any eligibility criteria.

- Patients with treatment deviation.

Protocol deviations other than those specified above may be identified. These will be identified using programmatic data checking where possible, supported by visual review of the data. These deviations will be categorised as either minor or major prior to database lock, at the BDRM prior to unblinding.

The **Safety Analysis Set** (SAF) consists of all patients who take at least one administration of study treatment. Patients will be analysed according to the treatment actually taken.

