6.11.1 Primary Analysis

Percentage change in MELD score from baseline up to and including day 28 will be assessed by modelling change from baseline with a mixed-model repeated measures (MMRM) analysis, using the FAS, including terms for treatment group, visit, treatment-by-visit interaction as fixed effects and the baseline MELD value as a covariate. The adjusted treatment least squares (LS) means and adjusted mean LS difference between the active dose and placebo will be presented along with 95% confidence intervals (CI) and p-value for the day 28 timepoint. Early termination data will be entered into the model at the next scheduled visit following the date of termination, not at day 28.

F-tests from PROC MIXED will be based on Kenward-Roger's adjusted degrees of freedom. The following variance/covariance matrix structures for the repeated visits within a patient will be assessed: Compound symmetry, 1st order autoregressive, Toeplitz and unstructured. The variance/covariance matrix structure that results in the smallest Akaike's information criterion (AIC), indicating the best model fit will be selected.

Assumptions of normality will be assessed visually using diagnostic plots. Should assumptions of normality not hold the model will be fitted to the change from baseline of log-transformed data. Should the assumptions behind the model still not hold an alternative approach to the analysis will be decided following the BDRM and will be detailed in a SAP amendment.

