6.12.1.2 Descriptive summaries and listing

Covered under section [16.7](#).

6.12.2 Proportion of patients showing a 25% reduction of bilirubin at Day 7, 14, 21 and 28

The proportion of patients showing a 25% reduction of total bilirubin at days 7, 14, 21 and 28 will be compared between treatment groups using a MMRM logistic regression model.

At each visit, patients with $\geq 25\%$ reduction in total bilirubin from baseline will be assigned a value of 1 (indicating 25% reduction achieved) while patients with a $< 25\%$ reduction will be assigned a value of 0 (indicating 25% reduction not achieved).

The model will include treatment, visit, treatment-by-visit as fixed effects and baseline bilirubin as a covariate.

The variance/covariance matrix structure that results in best model fit will be selected using the process described in section [6.11.1](#). The adjusted LS estimate for the treatment odds of achieving the endpoint and treatment odds ratio (DS102:Placebo) and corresponding 95% CIs and p-value corresponding to the treatment odds ratio will be presented.

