6.12.6.2 Descriptive summaries and listing

MDF score observed values, absolute change from baseline and percentage change from baseline will be listed and summarised by treatment group and visit.

6.12.7 Proportion of patients showing a 25% reduction in MELD score from baseline to Day 7, 14, 21 and 28

The proportion of patients showing at least a 25% reduction in MELD score at days 7, 14, 21 and 28 will be compared between treatment groups using a MMRM logistic regression model.

At each visit, patients with $\geq 25\%$ reduction from baseline will be assigned a value of 1 (indicating 25% reduction achieved) while patients with a $< 25\%$ reduction will be assigned a value of 0 (indicating 25% reduction not achieved).

The model will include treatment, visit, treatment-by-visit interaction as fixed effects and baseline MELD score as a covariate.

The variance/covariance matrix structure that results in best model fit will be selected using the process described in section [6.11.1](#).

The adjusted LS estimate for the treatment odds of achieving the endpoint and treatment odds ratio (DS102:Placebo) along with corresponding 95% CIs and p-value (corresponding to the treatment odds ratio) will be presented at days 7, 14, 21 and 28.

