6.12.10.1 Analysis

The proportion of patients showing a 2-point worsening/increase in m-SOFA score at days 7, 14, 21 and 28 will be compared between treatment groups using a MMRM logistic regression model.

At each visit, patients achieving a ≥ 2 -point increase in m-SOFA score from baseline will be assigned a value of 1 (indicating a 2-point worsening) while patients achieving < 2 -point increase in MELD score will be assigned a value of 0 (indicating not a 2-point worsening).

The model will include treatment, visit, treatment-by-visit interaction and baseline m-SOFA score as a covariate.

The variance/covariance matrix structure that results in best model fit will be selected using the process described in section [6.11.1](#).

The adjusted LS Means for the treatment odds of achieving the endpoint and treatment odds ratio (DS102:Placebo) along with corresponding 95% CIs and p-value (corresponding to the treatment odds ratio) will be presented at days 7, 14, 21 and 28.

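### No rule chosen for death stands beside the primary MELD analysis or in the responder models, and the SAP changes the MELD/death composite without declaring it

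*SAP*

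**What the plan says.** - **Primary model.** SAP 6.11.1 assesses MELD "with a mixed-model repeated measures (MMRM) analysis, using the FAS, including terms for treatment group, visit, treatment-by-visit interaction as fixed effects". Its only rule for incomplete data places early termination values at the next scheduled visit.
- **Sensitivity analyses.** SAP 6.11.2 repeats the model in the PPS and then says "Missing MELD data will be imputed using a last observation carried forward approach". Under SAP 6.4, PPS patients must "Have complete MELD score data at baseline and day 28/early termination visit".
- **General rule.** SAP 6.3 defers: "Imputation of any data will be detailed in the relevant sections". Sections 6.11.1, 6.11.2, 6.12.2, 6.12.7 and 6.12.10 do not mention death.
- **Responders.** In 6.12.2 a patient whose bilirubin falls by less than 25% "will be assigned a value of 0 (indicating 25% reduction not achieved"). In 6.12.7, "The proportion of patients showing at least a 25% reduction in MELD score at days 7, 14, 21 and 28 will be compared" on the same 0/1 basis. In 6.12.10 a patient with less than a 2-point rise "will be assigned a value of 0 (indicating not a 2-point worsening"). SAP 6.1 bases categorical percentages on non-missing observations, and its exceptions do not include these tables.
- **Composite.** Protocol 12.8.3: "A new secondary efficacy variable will be a 5-level ordinal variable combining change of MELD score from baseline", treatment termination and mortality. It divides level 4 from level 5 by whether MELD improved, with no threshold. SAP 6.13.7 lists the variable under exploratory endpoints and defines improvement as a reduction of at least 25%. SAP 6.25 lists four departures from the protocol; neither of these is among them.
- **Where death is counted.** Cox and Kaplan-Meier analyses (SAP 6.13.1), composite levels 1 and 2 (6.13.7), and TEAEs leading to death (6.16.1).

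**The concern.** Protocol 1.1 describes a disease with mortality above 30%, and SAP 6.11 calls MELD a good predictor of 90-day mortality. Deaths before Day 28 are therefore foreseeable and likely to be related to MELD. With no chosen rule, each analysis handles them by default, and no default counts death as worse than a poor MELD.

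If the drug lowered MELD but also raised deaths, the MMRM, its two sensitivity analyses and the responder odds ratios could all read as benefit. The deaths would appear only in separate outputs. The composite is the one planned analysis that joins MELD and death, and it no longer matches the protocol.

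**Working it through.** **1. The plan's own figure.** Protocol 12.3 gives 55 per group for d = 0.54, two-sided alpha 0.05. The exact noncentral-t power with 108 degrees of freedom is 0.8014, as printed. The sample size is not in question. The step from 55 to 60 allows for 5/60 = 8.3% loss, and death is not mentioned.

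**2. What happens to a patient who dies on Day 10.**

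| Analysis | Default handling |
|---|---|
| MMRM | later MELD missing at random |
| LOCF | Day 7 MELD carried to Day 28 |
| PPS | dropped unless an early termination MELD exists |
| 25% responders, Days 14 to 28 | not in numerator or denominator |
| m-SOFA worsening, Days 14 to 28 | not in numerator or denominator |

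**3. Size for the primary endpoint (simulation; all inputs assumed).** There are 60 patients per arm and 800 trials per scenario (Monte Carlo error at most 1.8 points). Baseline MELD has mean 25 and SD 5, truncated at 18. The mean placebo change is about -8%, and the SD of percentage change is 23.5. The drug effect is -12.5 points (12.5/23.5 = 0.53 SD), building linearly to Day 28. Death hazard rises 18% per MELD point at the last visit, and no other data are missing. The MMRM used an unstructured covariance and n - 3 degrees of freedom rather than Kenward-Roger. The ranked analysis puts deaths below all survivors and adjusts for baseline MELD. Chance of significance for the drug:

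| Day 28 deaths, placebo/drug (%) | MMRM | LOCF | Ranked |
|---|---|---|---|
| 10/5 | 80% | 83% | 82% |
| 15/15 | 77% | 74% | 50% |
| 10/20 | 75% | 62% | 21% |
| 15/30 | 70% | 50% | 5% |
| 30/15 | 75% | 85% | 87% |

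LOCF moves part of the way because it carries earlier, smaller effects forward, not because it counts death. A simpler simulation comparing survivors by ANCOVA gave 81 to 90% against 5 to 6% ranked at 15/30.

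MMRM bias was at most 0.015 SD. With a steeper link (hazard +30% per point) and deaths 5/30, it was 0.07 to 0.08 SD towards the drug, and the false-claim rate for the drug was 7.0% instead of 2.5%.

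**4. Size for the responders.** With no MELD effect and deaths 15/30, the simulated 25% MELD responder rates among observed patients were 24.3% placebo and 26.3% drug.
- Observed only: OR = (26.3/73.7)/(24.3/75.7) = 1.11.
- Deaths as not achieved: 24.3 × 0.85 = 20.7% and 26.3 × 0.70 = 18.4%, so OR = (18.4/81.6)/(20.7/79.3) = 0.86. The direction reverses.
- m-SOFA, if 10 to 16% of survivors worsen in both arms: placebo 15 + 0.85 × (10 to 16) = 23.5 to 28.6%; drug 30 + 0.70 × (10 to 16) = 37.0 to 41.2%.

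**5. The composite cut.** A fall in MELD from 25 to 20 is -20%: improvement in the protocol, no improvement in the SAP. If percentage change is normal with mean m and SD s, the share moved from level 5 to level 4 is Φ((0 - m)/s) - Φ((-25 - m)/s). For m = -10, s = 20: 0.691 - 0.227, about 0.465. Over m from -5 to -30 and s of 20 or 30, the range is 0.275 to 0.465.

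**6. The day count.** SAP 6.13.1 adds 1 to death date minus randomisation date. Protocol 8.2.3 places randomisation and the first dose at Baseline, which is Day 0. A Day 28 death has survival time 28 - 0 + 1 = 29. It falls into level 2 if within 28 days means 28 or less. By the same count a Day 90 death has time 91.

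**The case against.** **What stands.**
- Deaths are covered by default: LOCF and the MMRM apply to any missing MELD. What is missing is a rule chosen for death.
- Mortality is not ignored. The Cox model and the composite count it, and the DSMB reviews accumulating data (Protocol 13.3). For detecting a death difference the Cox model is the better tool: at 15/30 there are 9 + 18 = 27 deaths by Day 28, a hazard ratio of about 2.19 and about 53% power, against 27% for the ranked analysis.
- The protocol is not consistent on the composite: 12.8.3 calls it secondary, but the endpoint lists in the synopsis and section 5.2 omit it. The 25% cut matches the responder threshold and cost no power in simulation. The SAP is based on protocol Version 4.0, and the version of the protocol supplied cannot be seen.
- The day-count point affects only deaths on the boundary day.

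**Readings that go too far.** A reader might infer that the MMRM is invalid. The simulations do not show that when death follows recorded MELD; bias appears only under a steep link with very unequal deaths. A reader might also take Protocol 12.8.3 to confine the missing-at-random assumption to loss to follow-up. That sentence only allocates lost patients within the composite, where deaths already hold levels 1 and 2; it does not restrict the primary model.

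**What does not stand.** The outputs that count death do not qualify the MELD estimate or the responder odds ratios. The 25% cut is more than an operational detail, because it reverses the label of every fall between 0 and 25%.

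**Conclusion.** The point holds as a gap in the supporting analyses and an undeclared change to the composite. It should be fixed, but it does not invalidate the primary analysis. There is no alpha consequence, since secondary and supportive analyses are descriptive and unadjusted (SAP 6.14).

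The missing rules and the undeclared changes follow from the text alone. The sizes do not: the documents give no Day 28 death rate, the mortality figure in Protocol 1.1 has no time horizon, and the exclusion criteria may lower it. On the assumptions used, handling of death hardly matters at 10/5 but decides the reading of the trial at 15/30. The MMRM result also assumes that death depends on MELD as recorded at the last visit. The 28 to 47% reclassification rests on a normal distribution of percentage change among survivors.

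**What to change.** 1. **Responder models.** In SAP 6.12.2 and 6.12.7, count death as not achieved at visits after death. In 6.12.10, count it as worsened, at least in a supplementary version. Keep patients who died in the FAS denominator of the matching tables.
2. **One supportive analysis in SAP 6.11.2.** On the FAS, rank deaths by Day 28 below all survivors and rank survivors by MELD change, adjusted for baseline MELD. State how survivors without a Day 28 MELD are imputed. The sponsor must first confirm the scale: Protocol 5.1 and SAP 2.2 say percentage change; Protocol 12.8.2 and SAP 6.11 say change; SAP 6.11.1 uses both terms. The simulation above used percentage change.
3. **Composite.** Use the protocol's improvement/no-improvement split and keep the 25% cut as supplementary. Reconcile secondary or exploratory status between Protocol 12.8.3, the endpoint lists and SAP 6.13.7. Declare any remaining change in 6.25 with its reason.
4. **Day count.** Define death within 28 and 90 days as death date minus randomisation date, without the added day.
5. **Display.** Show deaths by arm beside the primary MELD result.

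The cost is SAP wording and a few programs on data already collected, since the flow charts record mortality at each visit from Day 3. The changes must be made before unblinding; SAP 6.2 already provides for an amendment. The ranked analysis is harder to interpret and loses power when deaths are equal (about 50 to 55% against about 77% at 15% per arm, under the assumptions), so it should stay a sensitivity analysis.

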6.13.6.2 Descriptive summaries and listing

Lille score observed values, absolute change from baseline and percentage change from baseline will be listed and summarised by treatment group and visit.

6.13.7 Combination of change of MELD score from baseline, premature treatment terminations and mortality

A 5-level ordinal variable combining change of MELD score from baseline, premature treatment terminations and mortality will be derived.

Each patient will be allocated to the lowest/worst level that occurred.

Level 1: death within 28 days using survival time derived in section [6.13.1](#)

Level 2: death within 90 days using survival time derived in section [6.13.1](#)

Level 3: early termination because of safety issues or lack of efficacy

Level 4: no improvement in MELD score at day 28 compared to baseline (classed as less than 25% reduction in MELD score from baseline to day 28).

Level 5: improvement in MELD score at day 28 compared to baseline (classed as greater than or equal to a 25% reduction in MELD score baseline to day 28).

Patients who are lost to follow up within 28 days and therefore do not have a day 28 MELD score will be allocated to level 4 or 5 depending on their imputed result at day 28 based on the model in section [6.11.1](#) under a missing at random (MAR) assumption.

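### The one planned check on missing MELD data for the primary endpoint carries the last value forward: it tests a single fixed alternative, cannot show how strongly the Day 28 result leans on missing at random, and can itself create a difference

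*SAP*

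**What the plan says.** The primary analysis (SAP 6.11.1) works by "modelling change from baseline with a mixed-model repeated measures (MMRM) analysis, using the FAS". It is likelihood-based, so it relies on missing at random (MAR) for unseen values. When a patient terminates early, "Early termination data will be entered into the model at the next scheduled visit following the date of termination, not at day 28".

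SAP 6.11.2 lists two sensitivity analyses:
- "The primary analysis will be repeated for the PPS". Among the conditions for the per-protocol set (SAP 6.4) is: "Have complete MELD score data at baseline and day 28/early termination visit".
- "Missing MELD data will be imputed using a last observation carried forward approach", after which the primary model is refitted with the filled-in values.

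On missing data in general, SAP 6.3 says only that "Imputation of any data will be detailed in the relevant sections". No delta-adjusted, reference-based, tipping-point or multiple-imputation analysis of the primary endpoint is planned.

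The five-level ordinal variable (SAP 6.13.7; Protocol 12.8.3) ranks deaths, and early terminations for safety or inefficacy, below every MELD outcome. Patients lost to follow-up before Day 28 get a value from the primary model "under a missing at random (MAR) assumption".

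**The concern.** The point concerns patients who are alive but have no Day 28 MELD: consent withdrawn, lost to follow-up, or visit missed. Deaths are a separate question.

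The primary model assumes that the unseen MELD of these patients follows that of comparable patients who stayed. The data cannot verify this, so the sensitivity analysis should vary it. The per-protocol repeat restricts the sample without varying the assumption. Carrying forward replaces MAR with one fixed guess, and one guess gives no scale on which to read the dependence.

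The guess can also mislead. SAP 6.11.1 declines to place an early-termination value at Day 28, but carrying forward moves that same value into the Day 28 cell. MELD is scheduled at Days 3, 5, 7, 14, 21 and 28 (Protocol 9.1.1), so a carried post-baseline value can be up to 25 days old. If MELD is falling, the arm that loses more patients, or loses them earlier, looks worse. A disagreement with the primary model could then be an artefact.

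**Working it through.** **The plan's own figure.** Noncentral-t power for two groups of 55, effect size 0.54, two-sided alpha 0.05, is 0.8014. This agrees with the table in Protocol 12.3. Going from 55 to 60 per group allows for at most 5/60 = 8.3% loss. That margin must also cover non-ideal distributions, and no loss rate is stated.

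**Assumed, because the documents give no values:** mean MELD trajectory, SD, within-patient correlation, and loss rates and timing.

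**Closed form for the false difference with no drug effect.** With losses unrelated to outcome and a linear mean fall,

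false difference = (share lost in arm 1 − share lost in arm 2) × fall by Day 28 × average fraction of the fall still to come at exit.

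Let the last observed visit be equally likely to be Day 3, 5, 7, 14 or 21. The average last day is 50/5 = 10, and the fraction still to come is (28 − 10)/28 = 0.643.

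| Lost per arm | Fall 3 | Fall 5 | Fall 8 |
|---|---|---|---|
| 7/60 v 3/60 (11.7% v 5%; 10/120 = 8.3% overall): 0.0667 × 0.643 × fall | 0.13 | 0.21 | 0.34 |
| 25% v 10%: 0.15 × 0.643 × fall | 0.29 | 0.48 | 0.77 |
| Equal shares, equal timing | 0 | 0 | 0 |

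**Simulation of the same settings.** The inputs were 4,000 trials per setting, 60 per arm, baseline MELD mean 25, SD 5 and correlation 0.4 + 0.6 exp(−days/14). Day 28 change was compared by ANCOVA after carrying forward.
- 11.7% v 5%: 0.13, 0.22 and 0.33 points; rejection 5–7%.
- 25% v 10%: 0.28, 0.46 and 0.77 points; rejection about 6–15% over the three trajectories, depending on simulation details.
- Equal 8.3% or equal 15%: no bias; rejection about 5%.

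**Timing alone is enough.** With 20% lost in each arm, last seen at Day 21 in one and Day 7 in the other, the fractions still to come are 7/28 = 0.25 and 21/28 = 0.75. The false difference is 0.20 × 0.50 × fall, which is 0.05, 0.10 or 0.15 SD for falls of 0.5, 1.0 or 1.5 SD. Simulated rejection was 6%, 8% and 12%. A likelihood estimate under MAR stayed within 0.01 SD of zero.

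**What a delta analysis would show.** If only missing DS102 values are shifted, the contrast moves by share lost × delta. At 15% lost, each MELD point moves it by 0.15 points. As an illustration, take an observed effect of 0.54 SD. The smallest significant difference at 60 per arm is about 0.3615 SD, so the tipping delta is (0.54 − 0.3615)/share lost, ignoring the extra variance from missing data:

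| Share lost on DS102 | Tipping delta (SD) |
|---|---|
| 8.3% | 2.14 |
| 15% | 1.19 |
| 20% | 0.89 |
| 30% | 0.60 |

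A single carry-forward run cannot supply this table.

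**The case against.** **The group is narrow.** Patients who stop only study drug keep their efficacy visits (Protocol 7.5.2), those leaving the study are asked for an early-termination visit (7.5), and losses to follow-up may be replaced (7.6). This stands, and it limits the size of the problem.

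**Large arm gaps are not anticipated.** The plan implies at most 8.3% loss, and at that level the artefact is small. This stands too, so the 25% v 10% figures illustrate the mechanism and are not a forecast.

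**Not every carried value is early.** A patient who terminates after Day 21 supplies an actual value in the Day 28 cell, and one last seen at Day 21 is carried a single visit. It would be wrong to read the plan as freezing every leaver near baseline.

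**A partial departure from MAR exists.** The five-level variable takes deaths and early terminations for safety or inefficacy outside MAR. However, it is a different outcome, sits among the exploratory endpoints in the SAP, and keeps MAR for losses to follow-up. It narrows the gap without closing it.

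**Agreement is still informative.** A reader might infer that agreement between the two analyses would show nothing. That goes too far: it would show robustness to one stated alternative, no change after exit.

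**The simulation is not the planned model.** It uses ANCOVA at Day 28, whereas the SAP refits the repeated-measures model with a covariance structure chosen by AIC. The exact rejection rates are therefore approximate.

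**Conclusion.** The point holds in this form. The only analysis of the primary endpoint that changes the missing-data assumption tests a single alternative, so it cannot show how far patients who leave alive must depart from MAR to change the Day 28 conclusion. This limitation needs no particular dropout scenario.

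The false difference is conditional. It requires a moving mean MELD together with losses that differ by arm in share or timing. Under the assumed trajectories it is about 0.1–0.3 points at the plan's implied overall loss and about 0.3–0.8 points at 25% v 10%. It vanishes with flat MELD or with equal losses of equal timing.

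A reader might infer that the trial's false-positive rate is inflated. The documents do not support that: the rejection rates above belong to a supporting table, and the primary test does not use carried-forward values. This is a worthwhile, inexpensive improvement and does not undermine the primary analysis.

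**What to change.** In SAP 6.11.2, make the missing-data sensitivity analysis a multiple imputation from the 6.11.1 model:
- Impute on the scale used for the primary analysis. The scale has to be settled first, because SAP 6.11.1 names percentage change, models change from baseline, and allows a log transformation.
- Add a delta (0, +2, +4, … MELD points, or the equivalent on that scale) to the imputed Day 28 values of DS102 patients who left alive, and combine by Rubin's rules.
- Report the estimate and confidence interval over a fixed, pre-stated delta range whatever the primary result, and the tipping delta if that result is significant.
- State that deaths before Day 28 are not given delta-imputed values and are handled by a separate stated rule.
- Drop the carry-forward analysis or keep it as descriptive only.

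The cost is SAP wording and slightly more programming, with no new data, visits or patients. SAP 6.2 already provides for an amendment before database lock. The downside is a range of results to present instead of one table.
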